3.5 Timing of Final Analysis

Final analysis will take place after all enrolled patients have either completed their six-month follow up visit or have withdrawn from the study.

3.6 Blinded analysis

This is not a blinded trial.

SAP Version No: V1.0 Date: 17Jun2021 SAP Author: [name] OCTRU-OST-001_V3.0_16Feb2018 Effective Date 23Feb2018

3.7 Statistical Analysis Outline

Section 18 (Statistical Analysis Plan) of the protocol includes the following:

All patients enrolled in the study and who received at least one dose of atovaquone will be accounted for and included in the analyses. The number of patients who were not evaluable, who died or withdrew before treatment began will be recorded. The distribution of follow-up time will be described, and the number of patients lost to follow-up will be given.

The analysis will include a description of patients who did not meet all the eligibility criteria, an assessment of protocol deviations, study drug accountability and other data that impact on the general conduct of the study.

Baseline characteristics will be summarised for all enrolled patients. Patients who died or withdrew before treatment started or do not complete the required safety observations will be described and evaluated separately. Treatment-related toxicity will be tabulated by type and grade of toxicity. All patients will be evaluable for toxicity from time of the first treatment. Adverse events will be summarised by the number of patients experiencing each type of event. The grades and causality will be reported.

4. STATISTICAL PRINCIPLES

4.1 Statistical Significance and Multiple Testing

There will be no statistical significance level defined for Arcadian as it is a dose-finding trial and dose recommendations will be based on the posterior probabilities calculated by the dose-toxicity model using all available data at each time.

4.2 Definition of Analysis Populations

The analysis population for the primary and secondary safety analysis is all patients who have received at least one dose of atovaquone. See Section 2.2 for the definitions of the analysis populations for the other endpoints.

Sensitivity analysis for the primary endpoint will be carried out including only patients who have received >75% of the full prescribed dose of atovaquone up to time of assessment. Patients who have had a DLT will be included irrespective of amount of atovaquone received.

5. TRIAL POPULATION AND DESCRIPTIVE ANALYSES

5.1 Representativeness of Study Sample and Patient Throughput

The flow of participants through each stage of the trial, including numbers of participants assigned to a schedule, receiving intended treatment, completing the study protocol, and analysed for the primary outcome will be provided following CONSORT. Protocol violations/deviations and information relating to the screening data including the number of ineligible patients entering the study, together with reasons will be reported. Information on number of participants screened, found to be ineligible (with reasons where available), refused to participate (with reasons where available) will also be included.

A CONSORT diagram will be prepared, an example CONSORT diagram is given in Appendix 3

5.2 Withdrawal from treatment and/or follow-up

Withdrawals/loss to follow-up together with reasons will be reported by atovaquone dose schedule. Also see Appendix 3.

5.3 Baseline Comparability

Baseline characteristics, including important demographic and clinical variables will be reported for all evaluable patients.

Numbers (with percentages) for binary and categorical variables and means (and standard deviations), or medians (with lower and upper quartiles) for continuous variables will be presented.

5.4 Unblinding

This trial is not blinded.

5.5 Description of Compliance with Intervention

A summary of the total amount of atovaquone received and the total amount of CRT received will be presented by assigned atovaquone dose schedule. Further detail related to compliance to atovaquone and each CRT component will be presented descriptively in tables and graphs. Any withdrawals from treatment or consent will be presented. See tables and graphs in Appendix 3.

5.6 Reliability

Safety and treatment compliance data will be regularly checked and cleaned, this may involve checking that data is complete e.g. not missing CTCAE grade and consistent across CRFs.

Variables derived from raw data using a computer program may be checked by hand for 5% of patients randomly sampled.

6. ANALYSIS

6.1 Outcome Definitions

Primary outcome

To determine the maximum tolerated dose (MTD), and therefore recommended phase II dose (RPTD), of atovaquone when combined with radical concurrent chemoradiotherapy

The outcome is the occurrence (yes/no) of a DLT within the DLT assessment period. For patients without a DLT, time observed within the DLT assessment period will also be taken into account in the analysis. The total i.e. maximum duration of the DLT assessment period for each patient is the length of the atovaquone run-in period (1-3 weeks) which will be pre-specified before the patient starts treatment, plus the length of CRT treatment (6.5 weeks= 45 days) plus follow-up duration (12 weeks = 84 days). At final analysis, patients without a DLT will have completed the DLT period unless they withdrew early. The MTD will be the dose level with posterior mean DLT rate closest to the target toxicity level of 48% when the dose-toxicity model is updated for the final analysis.

For the definition of a DLT, see Appendix 4.

Secondary outcomes

To assess the safety and toxicity profile of atovaquone in combination with radical concurrent chemotherapy

Adverse events from the first dose of atovaquone to six months post completion of CRT will be presented (see Appendix 3).

To confirm feasibility of measuring hypoxia metagene signature using 3'RNA-Seq in diagnostic NSCLC samples

To assess agreement of FMISO PET-CT with plasma miR-210 level and tumour hypoxia gene expression pretreatment with atovaquone

Hypoxia assessed using the baseline FMISO PET-CT scan will be measured using tumour to blood ratio (TBRvolume) (ml).

Plasma miR-210 level will be derived from the baseline blood sample.

Baseline is at week -2/-3 prior to receiving the first dose of atovaquone.

To assess agreement in changes in FMISO PET-CT and plasma miR-210 level following two weeks (+/- 7 days) of atovaquone

Change in FMISO PET-CT will be the % change between TBRvolume (ml) derived from the baseline and pre-CRT scans.

Change in plasma miR-210 level will be the % change between miR-210 level derived from the baseline and pre-CRT blood samples.

Baseline is at week -2/-3 prior to receiving the first dose of atovaquone and pre-CRT is at week -1 (two weeks (+/- 7 days) after starting atovaquone and prior to receiving any CRT.

To assess the tumour response rate at three months following treatment

Tumour response will be measured according to the RECIST V1.1 criteria, this endpoint will be the response taken at the assessment three months after the completion of CRT (at 13-15 weeks post-CRT).

Response will be classified as complete response (CR), partial response (PR), stable disease (SD), progressive disease (PD) or "not evaluable" (NE), as measured from their baseline scan to three months post-CRT scan. See Appendix 2 of the protocol for response category criteria.

The protocol states 'To be assigned a status of complete response (CR) or partial response (PR), changes in tumour measurements must be confirmed by two observations at least 4 weeks apart.' The Chief investigator has confirmed that it was never the intention for patients to receive a second scan to confirm CR/PR status, furthermore it is not standard of care and it is not included in the MPE dose assessment or IRAS application, so it cannot be done with our current ethics so the disease response will only be taken at the three months post CRT visit. There is currently no plan to update the protocol to amend this minor error.

To be assigned a status of stable disease (SD), tumour measurements must have met the SD criteria at least once, a minimum of six weeks after study treatment is started.

Should rapid tumour progression occur before the completion of treatment, the patient will be classified as having early progression (EP).

Tumour response should be classified as "not evaluable" (NE), only when it is not possible to classify it under another response category (e.g., when baseline and/or follow-up assessment is not performed or not performed appropriately).

Exploratory outcomes

To assess the relationship between plasma atovaquone levels and hypoxia response as measured by FMISO PET-CT and plasma miR-210 level

Plasma atovaquone levels (μ M) will be derived from the pre-CRT blood samples.

Hypoxia response will be measured using TBRvolume (ml) derived from the baseline and pre-CRT FMISO PET-CT scans.

Plasma miR-210 level will be derived from the baseline and pre-CRT blood samples.

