23.4	URGENT SAFETY MEASURES	
23.5	TEMPORARY HALT	
23.6	Serious Breaches	
23.7	TRIAL REPORTS	
23.8	TRANSPARENCY IN RESEARCH	50
24	EXPENSES AND BENEFITS	50
25	QUALITY ASSURANCE	50
25.1	Risk assessment	
25.2	Monitoring	50
25.3	AUDIT AND REGULATORY INSPECTION	51
26	RECORDS RETENTION & ARCHIVING	
27	PATIENT CONFIDENTIALITY	
28	STUDY FUNDING	
29	SPONSORSHIP AND INDEMNITY	
29.1	Sponsorship	
29.2	INDEMNITY	
29.3	CONTRACTS/AGREEMENTS	52
30	PUBLICATION POLICY	
31	REFERENCES	
APPENDI	IX 1: ECOG PERFORMANCE SCALE	
APPENDI	IX 2: MEASUREMENT OF DISEASE - RECIST CRITERIA	
APPENDI	IX 3: AMENDMENT HISTORY	

PROTOCOL SYNOPSIS

Full Title of study:	A Phase I Trial of the Hypoxia Modifier Atov	-				
Short Title:	Concurrent Chemoradiotherapy in Locally A	-				
Trial Acronym:	Atovaquone with Radical ChemorADIotherapy in locally Advanced NSCLC ARCADIAN					
Clinical Phase:	Phase I					
Study Design:	Single arm, open-label trial utilising Time To Event Continual Reassessment Method					
Study Design.	(TITE-CRM)					
	Objectives	Endpoints				
Primary Endpoint:	To determine the maximum tolerated dose (MTD), and therefore recommended phase II dose (RPTD), of atovaquone when	The dose of atovaquone associated with no more than 48% dose limiting toxicity (DLT) rate (target toxicity level)				
	combined with radical concurrent chemoradiotherapy in patients with non- small cell lung cancer (NSCLC)					
Secondary Endpoints:	To assess the safety and toxicity profile of atovaquone in combination with radical concurrent chemotherapy for NSCLC	Adverse events graded per Common Terminology Criteria for Adverse Events (CTCAE) v4.03				
	To confirm feasibility of measuring hypoxia metagene signature using 3'RNA- Seq in diagnostic NSCLC samples	Hypoxia metagene signature from diagnostic tissue using 3'RNA-Seq				
	To assess agreement of FMISO PET-CT with plasma miR-210 level and tumour hypoxia gene expression pre-treatment with atovaquone	 Tumour hypoxic volume determined by FMISO PET-CT Plasma miR-210 level Hypoxia metagene signature from diagnostic tissue using 3'RNA-Seq 				
	To assess agreement in changes in FMISO PET-CT and plasma miR-210 level following two weeks (+/- 7 days) of atovaquone	 Tumour hypoxic volume determined by FMISO PET-CT Plasma miR-210 level 				
	To assess the tumour response rate at three months (13-15 weeks) following treatment	Response to treatment assessed per Response Evaluation Criteria in Solid Tumours (RECIST) V1.1				

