17 STATISTICAL CONSIDERATIONS

17.1 Study design

This is a phase I, single arm, open label, two-centre study. The primary objective is to identify the MTD, and thus RPTD, of atovaquone when combined with concurrent CRT in NSCLC using a Bayesian TiTE-CRM design.

The CRM is a model-based method for finding the maximum tolerated dose (MTD) under the defining monotonicity assumption which posits that toxicity increases monotonically with increasing dose, and that efficacy also increases with increasing dose. The objective is to find the dose with a probability of experiencing a Dose Limiting Toxicity (DLT) close to a pre-specified target toxicity level. The TiTE-CRM is a modified version of the CRM that allows late-onset toxicities to be accounted for without fully observing a patient before recruiting the next and is therefore particularly advantageous for radiotherapy trials where toxicities are often observed later than in studies using systemic therapy alone. A major advantage of the TiTE-CRM is the fact that it uses all current accumulated information to decide which dose to assign the next patient. A further advantage of this design is that it will be able to include partial information on patients who could not be formally evaluated for DLTs due to withdrawal, treatment discontinuation or death, that is unrelated to treatment within the DLT assessment period (from week-2/-3 to three months post-CRT). In addition, the method results in shorter study duration as it is not necessary for a patient to be observed for the full observation period before recruiting the next patient, and also more patients are treated close to the MTD.

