Toxicity will be scored according to NCI CTCAE v4.03 with DLT definition as stated in Section 9. The trial aims to identify the MTD which is the dose associated with no more than 48% DLT rate (target toxicity level). This is based on the fact that standard concurrent CRT for NSCLC is often associated with a significant Grade \geq 3 toxicity rate. Average rates of Grade \geq 3 oesophagitis are in the region of 25%, although reported rates are variable and can be as high as 48%. In addition, rates of Grade \geq 3 pneumonitis as high as 32% have been reported and haematological toxicity when using platinum-doublet chemotherapy can also be significant in this patient population [22]. The atovaquone treatment schedule lasts for up to 9.5 weeks, with patients followed up at the end of the DLT assessment period (at three months post-CRT). An additional follow-up occurs a further three months later (at six months post-CRT), to provide a total trial observation window of up to 38 weeks.

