17.2 The TiTE-CRM model

A two-parameter Bayesian logistic model with weak priors will be used. The priors are calibrated to ensure the model provides sensible recommendations early in the trial. With this model we can obtain a distribution for the probability of DLT rate given a specific dose d based on all available data. This is a posterior probability distribution for dose d. We write P(T>0.48 | Data, dose = d) to mean the posterior probability that the DLT rate is greater than 48% on dose d, given the data observed so far.

At each dose decision (to assign a dose to the next patient), data for patients who have completed the DLT assessment period or experienced a DLT will contribute full information to this model. Only partial information is known for patients who are currently on trial, within the DLT assessment period, or have stopped treatment in the DLT assessment period for reasons other than a DLT. This partial information contributes to the model, weighted proportionally to the observed portion of their toxicity time window and treating them as not experiencing a DLT.

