17.3 Dose selection during the trial

The trial will start at the lowest dose of atovaquone (Dose 1: 450 mg BD). Two participants will receive this dose and escalation will only be considered when we have at least 12 weeks of safety data (high risk period of developing DLT) for at least one participant at this dose level, thus preventing inappropriate early dose escalation. Following this initial safety run in, all eligible patients will be continuously recruited. The TiTE-CRM model will be fitted every time a new patient is registered to recommend the dose of atovaquone from the possible doses: 450 mg, 600 mg, 675 mg or 750 mg. The dose recommended will be the dose with posterior mean DLT rate closest to the target toxicity level, subject to no dose skipping.

In order to escalate to a higher dose of atovaquone, there must be at least one patient on the previous highest dose who fulfils the following criteria:

- Completed ≥1 full cycle of CRT (i.e. at least three weeks of RT)
- Received ≥50% the specified dose of cisplatin
- Taken ≥75% their allocated dose of atovaquone
- Not experienced a DLT

The data provided to the model is binary (1 or 0 for experiencing a dose limiting toxicity or not) and thus information about severity of toxicities is not used. Whilst the model is carefully designed to make sensible decisions based on what the TMG would do in a certain situation, ultimately, the model and decision rules act as a guide. All dose recommendations made by the model will be reviewed by the TMG. The TMG will meet in person, teleconference, or via correspondence, and either approve the dose allocation recommendation or select a different dose on the basis of clinical review of the data. Additionally, since the window to observe toxicities is long, the TMG may opt to pause recruitment whilst on-trial patients complete their treatment. The trial will stop for safety if there is sufficient evidence to suggest that the lowest dose is too toxic. More specifically, we will consider dose level 1 to be too toxic if, given all the available data, there is a high probability that the DLT rate is greater than the target toxicity level of 48%.

We considered a number of scenarios to ensure that the trial design was appropriate. For each scenario, 1000 simulations were performed to assess and improve the model-based trial design. Full details of the simulated performance of the design under these scenarios are available in the Statistical Analysis Plan.

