17.5 MTD and RPTD definition

The MTD will be the final recommended dose after the trial has completed recruitment using all data accumulated in the trial. The MTD will constitute the recommended phase II dose (RPTD).

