17.6 Stopping the trial

The trial will stop for safety if there is sufficient evidence that the lowest dose is too toxic (if P(T>0.48 | dose = 1, current data) > 0.7).

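### The primary endpoint puts the MTD's DLT rate at or below 48%, but the selection rule takes the dose nearest 48% on either side

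*SAP*

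**What the plan says.** Both documents carry two descriptions of the MTD.

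**A ceiling.** The protocol synopsis, Protocol 3 and SAP 2.2 give the primary endpoint as "The dose of atovaquone associated with no more than 48% dose limiting toxicity (DLT) rate (target toxicity level"), and Protocol 17.1 says "The trial aims to identify the MTD which is the dose associated with no more than 48% DLT rate".

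**A nearest-distance rule.** Protocol 17.1 states the general aim of the CRM as to "find the dose with a probability of experiencing a Dose Limiting Toxicity (DLT) close to a pre-specified target toxicity level". Protocol 17.3 makes this operative: "The dose recommended will be the dose with posterior mean DLT rate closest to the target toxicity level, subject to no dose skipping". SAP 6.2 repeats that rule, and SAP 6.1 defines the MTD by it: "The MTD will be the dose level with posterior mean DLT rate closest to the target toxicity level of 48" per cent.

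Protocol 17.5 and SAP 6.2 make the final recommended dose the MTD. Protocol 17.5 adds: "The MTD will constitute the recommended phase II dose (RPTD").

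The only model-based toxicity limit is the early stopping rule: "The trial will stop for safety if there is sufficient evidence that the lowest dose is too toxic", meaning a posterior probability above 0.7 that the DLT rate at dose 1 exceeds 48% (Protocol 17.6, SAP 3.4 and 6.2).

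**The concern.** A ceiling and a nearest-distance rule are different criteria. Under the rule, a dose estimated somewhat above 48% beats a dose estimated further below it. The stated endpoint would then describe the recommended phase II dose as being within 48% while the trial's own estimate lies above 48%. A reader who knows only the endpoint would draw a stronger safety conclusion than the analysis supports.

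The figure is one readers may well treat as a limit. Protocol 17.1 supports it with the top of a reported range for severe oesophagitis, and Protocol Appendix 3 records that the regulator asked for it to be lowered from 50%.

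**Working it through.** The plan states no figure on this point to reproduce, so the check has four steps: what binds the final choice, the algebra of the rule, an illustration, and the limits on frequency.

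**1. What binds the final choice**

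| Provision | Where | Caps the declared MTD at 48%? |
|---|---|---|
| Endpoint wording | Synopsis; Protocol 3, 17.1; SAP 2.2 | Says so, but gives no selection method (neither highest dose nor posterior mean is mentioned) |
| Selection rule | Protocol 17.3; SAP 6.1, 6.2 | No; distance only |
| Stopping rule | Protocol 17.6; SAP 3.4, 6.2 | No; dose 1 only, at probability above 0.7 |
| TMG review | Protocol 17.3; SAP 3.4 | No numerical limit; written for each patient's allocation |

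**2. Cut-off (no priors needed)**

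Let the lower dose have posterior mean m_low < 0.48 and the next dose m_up > 0.48. The upper dose is chosen when

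m_up − 0.48 < 0.48 − m_low, that is, m_up + m_low < 0.96.

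- With m_low = 0.40, any m_up below 0.96 − 0.40 = 0.56 is accepted.
- With m_low = 0.30, any m_up below 0.96 − 0.30 = 0.66 is accepted.

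**3. Illustration with the SAP 6.2 model**

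Model: logit(θ) = log(α) + β·log(x/d*), with doses coded x = 1 to 4 and d* = 1. Full follow-up is taken, so every weight is 1. The real priors are in SAP Appendix 1, not supplied, so four are **assumed**, with log α and log β independent normal:

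- A: prior median DLT rate at level 1 of 0.25, SD of log α 2; log β mean 0, SD 1
- B: 0.40, 1; 0, 1
- C: 0.33, 1.5; −0.5, 0.7
- D: 0.25, 1; −0.5, 0.5

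Assumed data: 4/12/4/0 patients (20 in total) with 1/6/3/0 DLTs on levels 1 to 4.

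| Quantity | A | B | C | D |
|---|---|---|---|---|
| Level 1 mean | 0.311 | 0.351 | 0.370 | 0.359 |
| Level 2 mean | 0.513 | 0.528 | 0.508 | 0.486 |
| Level 3 mean | 0.636 | 0.630 | 0.590 | 0.562 |
| Level 2 SD | 0.110 | 0.105 | 0.107 | 0.102 |
| Level 1 + level 2 means | 0.825 | 0.879 | 0.878 | 0.845 |
| P(T > 0.48), level 2 | 0.62 | 0.67 | 0.60 | 0.52 |
| P(T > 0.48), level 1 | 0.12 | 0.15 | 0.18 | 0.13 |

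All four sums are below 0.96. Level 2 lies 0.006 to 0.048 from 0.48, level 1 lies 0.11 to 0.17 away and level 3 lies 0.08 to 0.16 away. Level 2 is therefore declared under every prior, 0.6 to 4.8 percentage points above 48%. Level 1 is far from the 0.7 stopping threshold.

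A second assumed dataset gives a larger excess: 2/4/8/6 patients with 0/1/4/5 DLTs.

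- Prior median 0.30, SD 2; log β mean 0, SD 1: level 3 is declared at 0.548, with P(T > 0.48) = 0.72.
- Prior median 0.40, SD 2; log β mean −0.5, SD 1: level 3 is declared at 0.541, with P(T > 0.48) = 0.70.
- Prior median 0.30, SD 1; log β mean −1, SD 1: level 2 is declared at 0.436, in a near tie with level 3 at 0.524.

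**4. Frequency**

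Simplified simulations were run with 1000 trials of 20 patients per scenario, full follow-up, no skipping, the dose-1 stopping rule and the first prior of the second dataset. The declared MTD had a posterior mean above 0.48 in 9.0% of trials (true rates 0.20/0.25/0.30/0.35) to 38.6% (0.30/0.40/0.52/0.62) across five assumed scenarios. These figures show that the event need not be rare. They are not this trial's operating characteristics.

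**The case against.** The strongest reply is that this is wording only. Nearest-to-target is the usual CRM rule, it gives one MTD, and no allocation or stopping decision would change. Each ceiling phrase is tagged as the target toxicity level, and Protocol 17.1 explains that the design seeks a rate close to target. This stands as to method: the procedure is valid. It does not remove the problem, because the tag softens the ceiling without cancelling it, and the ceiling is the stated primary endpoint in both documents.

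Second, the endpoint concerns the dose's true DLT rate, whereas the rule acts on an estimate from 20 patients. A mean of 0.49 to 0.53 with SD about 0.10 does not show that the true rate exceeds 48%, and a mean below 48% would not prove the reverse. That is fair. What remains is that nothing in the rule pulls the choice towards the ceiling side.

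Third, the illustration is selected and the excess is modest, under half a posterior SD (at most 0.048/0.105 = 0.46). With one fewer DLT on level 2 (1/5/3/0), the level 2 mean falls to 0.443 to 0.482. It is then above 48% only under prior B, by 0.2 points, although under prior D levels 2 and 3 tie to three decimals (0.443 + 0.517 = 0.960). The size is indeed sensitive to the data; the possibility is not.

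Fourth, the TMG reviews every recommendation, SAP 3.4 lets it choose a lower dose, and the Safety Review Committee stands behind it. This is a real safeguard for patients, but it sets no numerical limit on the declared MTD.

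**Conclusion.** The concern holds. Four places describe the MTD as having a DLT rate within 48%. The rule that selects it has no such bound, and no other provision supplies one above dose 1. That the declared dose can be estimated above 48% follows from the algebra alone. The sizes shown, 0.6 to 4.8 points in the main example and 6.1 to 6.8 points under two of three priors in the second (0.541 − 0.48 and 0.548 − 0.48), rest on assumed priors and data. The frequency in this trial cannot be derived from the documents supplied. The fault is a property claimed by the primary endpoint that the design does not have. It is not an invalid analysis, and it should be corrected because the result sets the phase II dose.

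**What to change.** Before the final analysis, reconcile the passages so that endpoint and rule state one criterion. The cheapest route keeps the rule and restates the endpoint in the synopsis, Protocol 3, Protocol 17.1 and SAP 2.2 as the dose with posterior mean DLT rate closest to the 48% target, which may lie above it.

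For the declared MTD, also report the posterior mean and P(T > 0.48 | data), unless the results tables already do so (SAP Appendices 2 and 3 were not supplied). Protocol 17.2 already defines the second quantity for any dose: "the posterior probability that the DLT rate is greater than 48% on dose d, given the data observed so far".

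Whether to impose a ceiling instead is a design trade-off for the sponsor and is not recommended either way here.

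The cost of the rewording is four edits, at most two extra reported numbers and possibly a protocol wording amendment. The analysis is unchanged. The price is a less reassuring endpoint statement.
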